## **Methods**

## Study design and patients

This will be a multicenter retrospective observational study carried out in Spain. In order to prevent selection bias in pharmacotherapy, participating centers will be selected if they use routinely a single IV PPI (esomeprazole or pantoprazole) in the management of PUB events.

The eligible patients will be all consecutive patients hospitalized due to PUB and selected according to codes from ICD9 which identify gastric and duodenal ulcer bleeding (Table I). Patients will be included retrospectively from

till completion of the desired sample size, which was estimated to be between ).

Eligible patients will be those complying with the following characteristics: a) age (≥18 years) admitted to the hospital with an overt upper GI bleed due to peptic ulcer and manifested as hematemesis/coffee ground vomiting, melena, hematochezia and other clinical or laboratory evidence of acute blood loss from the upper GI tract; b) evidence that an upper GI endoscopy was performed; c) IV PPI (esomeprazole or pantoprazole) had to be used after the endoscopy procedure d) complete medical records available for the study-related

3

hospitalization. Exclusion criteria are: patients with terminal malignant disease (life expectancy less than 6 months), required treatment with ASA or NSAIDs for the next 3 days during hospital after endoscopic therapy, or suffering from haematological disease associated with severe dyscrasia (e.g haemophilia)

Information regarding patient's characteristics, drug use before the PUB event, co-morbidities, symptoms, signs and severity of the event at hospital admission, endoscopic findings, endoscopic therapy, pharmacological therapy including type of drug, dose, route an type of administration, and outcomes will be collected from each patient's hospital medical records.

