## Data, measurements and endpoint definitions

We will collect data recorded in charts in a pre-specified Case Report Form. Main data from each patient will include demographics, diagnostic procedures and both non-pharmacological and pharmacological treatments received by patients as summarized in Table II.

Therapeutic endoscopy will be considered any endoscopic action (injection, clips, thermo-coagulation, etc...) implemented to control the bleeding event in the presence of spurting bleeding, oozing bleeding, visible vessel, and/or clots attached to the ulcer niche. Endoscopic re-treatment will be considered when any repeated procedure occurred within 30 days from the index hospital admission due to re-bleeding from the PUB episode. High-dose IV PPI will be considered the administration of either esomeprazole or pantoprazole by infusion at the dose of 8 mg/hour. However, due to the variability of clinical practice and for the purpose of this study, the administration of equivalent doses of the PPI by injection within each 24-hour period will also be considered. The dose, route and type of administration will be recorded for each patient.

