## Main outcomes:

- a) Bleeding continuation up to 3 days
- b) Re-bleeding at 3, 7 and 30 days
- c) Surgery at 3, 7 and 30 days
- d) Mortality at 3, 7 and 30 days

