## Definitions for outcome endpoints:

- a) Bleeding continuation up to 3 days after initial treatment:
  - 1. Spurting from an artery at the initial endoscopic examination which did not respond to endoscopic therapy.
  - 2. Persistence of bleeding following initial endoscopy determined by the presence of a red bloody naso-gastric aspirate, and/or shock with a pulse greater than 100 beats/min, a systolic blood pressure of under 100 mmHg, or both, and/or the need for substantial replacement of blood and fluid volume (transfusion of more than 3 units of blood within 4 h.) following endoscopic therapy and aimed to maintain the hemodynamic stability.
- b) Re-bleeding at 3, 7 and 30 days is defined, following initial successful endoscopic treatment, including resuscitation if indicated, as recurrent vomiting of fresh blood, melena, or both with either shock or a decrease in haemoglobin concentration of at least 20 g/l This could occur during the same hospitalization and after discharge (up to 30 days from the PUB episode).
- c) Surgery at 3, 7 and 30 days: the need of surgical intervention to control the bleeding event. This could occur during the same hospitalization and after discharge (up to 30 days from the PUB episode).
- d) Mortality at 3, 7 and 30 days: Death of patients during hospitalization (inhospital mortality) or after discharge (up to 30 days from the PUB episode).

- 1. Deaths will be related to the bleeding event: death from uncontrolled bleeding, death within 72 hours of endoscopy, death during surgery for uncontrolled bleeding, death from surgical complications or endoscopic-related death.
- Deaths will be considered unrelated to the bleeding event if them were due to cardiac, cerebro-vascular, pulmonary or terminal malignant diseases or multi-organ failure causes.
- e) Other outcomes will include days of hospitalizations, need of blood units transfused (total number).

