## Death:

A.- Bleeding-related death

- A1.- Died from uncontrolled bleeding.
- A2.- Died within 72h of endoscopy.
- A3.- Died during surgery for uncontrolled bleeding.
- A4.- Died from surgical complications or within one month of surgery
- A5.- Died from endoscopic-related mortality.
- B.- Non- bleeding related death
- B1.- Died of cardiac causes.
- B2.- Died of pulmonary causes.
- B3.- Died of cerebrovascular diseases.
- B4.- Died of multi-organ failure (including liver and kidney failure).
- B5.- Died of terminal malignant diseases.

Total number of units of blood transfused

Diagnostics test performed during hospitalization

Discharge date and admission date

Page left intentionally blank

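### Thirty-day re-bleeding, surgery and mortality include events after discharge, but no source is named for events outside the hospital record, so these rates may be too low by an amount the protocol cannot bound

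*Protocol*

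**What the plan says.** **Design and source.** "This will be a multicenter retrospective observational study carried out in Spain" (Protocol, Study design and patients). The same section says that "outcomes will be collected from each patient's hospital medical records", and Data, measurements and endpoint definitions adds: "We will collect data recorded in charts in a pre-specified Case Report Form". No registry linkage, primary-care record or patient contact is named.

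**Eligibility.** A patient must have "complete medical records available for the study-related" hospitalisation. Nothing is required of the record after discharge.

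**Outcome window.** Main outcomes lists "Mortality at 3, 7 and 30 days", with the same three time points for re-bleeding and surgery. Under Definitions for outcome endpoints, re-bleeding and surgery each carry the sentence "This could occur during the same hospitalization and after discharge (up to 30 days from the PUB episode"), and mortality is defined as "Death of patients during hospitalization (inhospital mortality) or after discharge (up to 30 days from the PUB episode").

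**Variables.** Table 2 gives the date of hospitalisation among patient characteristics and "Discharge date and admission date" at its end. It lists no day-30 status and no date of last contact.

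**Analysis.** The Statistics section reports categorical data as frequencies and proportions. It gives no rule for a patient whose status after discharge is unknown.

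**The concern.** The outcome window runs to day 30 whether or not the patient is still in hospital, while the only named source is what a hospital wrote down. The two match while the patient is an inpatient. After discharge they match only if the event brings the patient back to a hospital whose records are read. A death at home, or re-bleeding or surgery elsewhere, has no stated way in.

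The Statistics section says that the aim is to provide outcome rates, so any shortfall falls on the study's main product, and a larger sample does not reduce it. With all included patients in the denominator, a missed event can only lower the rate. Nothing in Table 2 separates a patient known to be alive at day 30 from one not heard of since discharge.

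Rates are also to be given by PPI, and centres are chosen because each routinely uses one PPI. Centres that differ in length of stay or in how well they pick up later events could therefore carry that difference into the by-PPI figures.

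**Working it through.** **1. The plan's own precision figure.** From the Statistics section: mortality p of about 5%, error d = 1.25 points for the lowest proportion, alpha 0.05, 1100 patients per PPI group.

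- n = 1.96² × p(1 − p)/d² = 3.8416 × 0.05 × 0.95/0.0125² = 1168.
- This is 6.2% above 1100. A rate of 4.7% gives 1100, so the wording that mortality is around 5% explains most of the gap.
- At n = 1100 and p = 5% the half-width is 1.29 points.

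The point here does not depend on this difference. The 1.25-point error serves only as a yardstick.

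**2. Size of a possible shortfall.** Let f be the share of 30-day events that occur after discharge, and m the share of those not in the chart. The protocol gives neither, so both are assumptions.

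- Observed rate = p(1 − f×m); loss = p × f×m.

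For a true 30-day mortality of 5%:

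| f | m | f×m | Observed | Loss (points) |
|---|---|---|---|---|
| 0.2 | 0.3 | 0.06 | 4.70% | 0.30 |
| 0.3 | 0.5 | 0.15 | 4.25% | 0.75 |
| 0.4 | 0.8 | 0.32 | 3.40% | 1.60 |

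- The loss equals 1.25 points when f×m = 1.25/5 = 0.25.
- For re-bleeding at 8%, the loss equals 1.25 points at f×m = 1.25/8 = 0.16, or the wider 2.5-point error at 2.5/8 = 0.31. The protocol does not say which error belongs to this rate.

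**3. Effect on a nominal 95% interval for mortality at n = 1100.** With observed rate r, loss b and se = √(r(1 − r)/1100), coverage is about Φ(1.96 − b/se) − Φ(−1.96 − b/se).

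- f×m = 0.10: r = 4.5%, b = 0.5 points, coverage about 87%.
- f×m = 0.20: r = 4.0%, b = 1.0 point, coverage about 60%.

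A loss smaller than the stated error can therefore still matter.

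**4. Would in-hospital rates be a better main outcome?** Take two centres with the same true 5% mortality, one with f = 0.2 and one with f = 0.4.

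- In-hospital rates: 5% × 0.8 = 4.0% and 5% × 0.6 = 3.0%, a spurious gap of 1.0 point.
- Chart-based 30-day rates with m = 0.5: 5% × 0.9 = 4.5% and 5% × 0.8 = 4.0%, a gap of 0.5 point.

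Moving to in-hospital outcomes makes the rates depend more on length of stay.

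**5. Which time points are exposed.** The mechanism acts only after discharge. Day-30 rates are most exposed. Day-7 rates are exposed for patients discharged before day 7. Day-3 rates should be little affected if few patients leave before then; the protocol gives no length of stay.

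**The case against.** The strongest reply is that the protocol never says unknown status counts as no event. A reader might infer that it does, but the Statistics section is silent, and such a rule is commonly left to an SAP, which is not at hand. This stands: the rates may be low, and have not been shown to be. An SAP could set the rule, but it could not supply a source or items that were never collected.

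Second, Table 2 is a summary and the CRF itself is not shown. A reader might infer from Table 2 that no event dates are captured. The text does not support that: outcomes are to follow definitions timed at 3, 7 and 30 days, and the death codes include death within 72 hours of endoscopy and within a month of surgery, so some timing must be recorded. What Table 2 gives no sign of is a day-30 status or a last-contact date.

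Third, the index-stay requirement is an entry minimum and does not limit which records are read. A reader might conclude that 30-day mortality here is simply in-hospital plus same-hospital readmission mortality. That is too definite: the hospital record is not confined to the index stay, or expressly to one hospital, and readmissions to the same hospital would normally be in it.

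Fourth, Data management and quality assurance has investigators check in advance, on a sample, that records suit the CRF, and has the CRFs monitored. This helps with what is in the chart. It cannot reveal a death that the hospital never learned of.

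Finally, the size is wholly assumed, and two of the three mortality scenarios lose less than 1.25 points. That also stands.

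**Conclusion.** The mismatch between outcome window and data source is explicit in the protocol. Events at home or in another hospital after discharge have no stated route into the data, so the 30-day rates may be too low, and nothing in the protocol bounds by how much. The direction follows from taking proportions of all included patients. The size does not follow from the documents: a true 5% reads between 4.7% and 3.4% over the assumed range, and the loss passes the stated error only once f×m exceeds 0.25.

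A reader might also infer that the by-PPI rates are distorted. That is a possibility created by choosing centres that use a single PPI; nothing in the protocol shows that stay or post-discharge capture differs between the two sets of centres.

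This should be put right because it changes what the day-30 figures can be said to estimate. It is no reason to drop them.

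**What to change.** Keep the 30-day outcomes and make these changes:

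1. Make sure the CRF records the dates of re-bleeding, surgery and death, and the date of last documented vital status or contact, from the same charts and including any later visit or readmission. If the prepared CRF already holds the event dates, only the last item is new. The bar on altering the CRF is addressed to the centres, so the change belongs in the common form before it is issued.
2. Report the number and share of patients with unknown day-30 status, overall and by PPI.
3. Either name a source for vital status and readmission after discharge, or label the day-30 rates as events recorded in hospital records up to day 30 (lower bound). Apply the same caution to day 7.
4. Show in-hospital rates alongside, not as the replacement main time frame.
5. As a sensitivity analysis, give 30-day mortality with known deaths by day 30 as the numerator, and those deaths plus patients documented alive at day 30 or later as the denominator. State that it leans high, because undocumented survivors drop out. For example, with 4.25% recorded deaths and, by assumption, half of the 95% true survivors documented, it gives 4.25/(4.25 + 47.5) = 8.2%.

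The cost is a few more items from charts already being read, some relabelled tables, and a weaker 30-day claim.

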## Data, measurements and endpoint definitions

We will collect data recorded in charts in a pre-specified Case Report Form. Main data from each patient will include demographics, diagnostic procedures and both non-pharmacological and pharmacological treatments received by patients as summarized in Table II.

Therapeutic endoscopy will be considered any endoscopic action (injection, clips, thermo-coagulation, etc...) implemented to control the bleeding event in the presence of spurting bleeding, oozing bleeding, visible vessel, and/or clots attached to the ulcer niche. Endoscopic re-treatment will be considered when any repeated procedure occurred within 30 days from the index hospital admission due to re-bleeding from the PUB episode. High-dose IV PPI will be considered the administration of either esomeprazole or pantoprazole by infusion at the dose of 8 mg/hour. However, due to the variability of clinical practice and for the purpose of this study, the administration of equivalent doses of the PPI by injection within each 24-hour period will also be considered. The dose, route and type of administration will be recorded for each patient.

## Main outcomes:

- a) Bleeding continuation up to 3 days
- b) Re-bleeding at 3, 7 and 30 days
- c) Surgery at 3, 7 and 30 days
- d) Mortality at 3, 7 and 30 days

## Definitions for outcome endpoints:

- a) Bleeding continuation up to 3 days after initial treatment:
  - 1. Spurting from an artery at the initial endoscopic examination which did not respond to endoscopic therapy.
  - 2. Persistence of bleeding following initial endoscopy determined by the presence of a red bloody naso-gastric aspirate, and/or shock with a pulse greater than 100 beats/min, a systolic blood pressure of under 100 mmHg, or both, and/or the need for substantial replacement of blood and fluid volume (transfusion of more than 3 units of blood within 4 h.) following endoscopic therapy and aimed to maintain the hemodynamic stability.
- b) Re-bleeding at 3, 7 and 30 days is defined, following initial successful endoscopic treatment, including resuscitation if indicated, as recurrent vomiting of fresh blood, melena, or both with either shock or a decrease in haemoglobin concentration of at least 20 g/l This could occur during the same hospitalization and after discharge (up to 30 days from the PUB episode).
- c) Surgery at 3, 7 and 30 days: the need of surgical intervention to control the bleeding event. This could occur during the same hospitalization and after discharge (up to 30 days from the PUB episode).
- d) Mortality at 3, 7 and 30 days: Death of patients during hospitalization (inhospital mortality) or after discharge (up to 30 days from the PUB episode).

- 1. Deaths will be related to the bleeding event: death from uncontrolled bleeding, death within 72 hours of endoscopy, death during surgery for uncontrolled bleeding, death from surgical complications or endoscopic-related death.
- Deaths will be considered unrelated to the bleeding event if them were due to cardiac, cerebro-vascular, pulmonary or terminal malignant diseases or multi-organ failure causes.
- e) Other outcomes will include days of hospitalizations, need of blood units transfused (total number).

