## **Objectives:**

1. To assess outcomes in clinical practice in patients hospitalized due to PUB and treated with high-dose IV infusion PPI plus standard endoscopy therapy in patients with endoscopic high risk stigmata (spurting bleeding, visible vessel, oozing bleeding, red clot attached to the ulcer niche): overall and among individual PPI (esomeprazole and pantoprazole).

2. To assess outcomes in clinical practice in patients hospitalized due to PUB and treated with IV infusion PPI plus endoscopy therapy, if needed: overall and among individual PPI (esomeprazole and pantoprazole).

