## **Statistics**

Sample size. Based on a recent international observational study on PUBs (Energib) the estimated re-bleeding rate was over 8% and the overall mortality rate of PUBs around 5%. It is assumed that these proportions will be increased between 1.5- and 2-fold in patients with high-risk stigmata that represent approximately between a third and a fourth of our total PUB study population. Assuming a 1.25% error for the lowest proportion and a 2.5% for the largest one, with an alpha value of 0.05, we have estimated a sample size of 1100 patients per group of PPI treatment for the overall PUB cohort to be studied and 400 - 500 per group (esomeprazole and pantoprazole) for those with high-risk stigmata.

Due to the study design, variables will be presented by descriptive statistics. Categorical data will be reported as frequencies and proportions. Continuous data will be reported as means and standard deviations. Where appropriate, alternate descriptive statistics such as quartile ranges, and medians with ranges for categorical and continuous data respectively will be reported. Analyses will be performed, overall, in patients with high-risk stigmata and according to individual PPI.

Although the objective of the study is to provide rates of outcomes of the different cohorts of PUB patients studied, potential differences in outcomes across different risk strata (age, co-morbidities, endoscopic findings, etc..) will be analysed with the Chi-square test for categorical variables and with t-test for continuous data. A variance analysis will be performed for multiple comparisons. Multivariable logistic regression models will also be fitted to define determinants of outcomes.

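### The only re-bleeding definition presupposes successful endoscopic treatment, so it does not fit the Objective 2 cohort, most of whom lack the stigmata to which that treatment is tied

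*Protocol*

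**What the plan says.** All references are to the protocol.

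- **Definitions for outcome endpoints, item b:** "Re-bleeding at 3, 7 and 30 days is defined, following initial successful endoscopic treatment, including resuscitation if indicated". The clinical criteria follow: vomiting of fresh blood, "melena, or both with either shock or a decrease in haemoglobin concentration of at least 20 g/l". No other re-bleeding definition appears, and no denominator is stated.
- **Objectives, item 2:** the cohort is patients hospitalized for PUB and "treated with IV infusion PPI plus endoscopy therapy, if needed".
- **Study design and patients:** eligibility asks for "evidence that an upper GI endoscopy was performed". It does not ask that any endoscopic therapy was given.
- **Data, measurements and endpoint definitions:** therapeutic endoscopy is an endoscopic action "implemented to control the bleeding event in the presence of spurting bleeding, oozing bleeding, visible vessel, and/or clots attached to the ulcer niche".
- **Statistics:** patients at high risk are those with "high-risk stigmata that represent approximately between a third and a fourth of our total PUB study population". For PUB in general, "the estimated re-bleeding rate was over 8% and the overall mortality rate of PUBs around 5" per cent, and both rates are assumed to rise 1.5- to 2-fold with high-risk stigmata. The targets are 1100 patients per PPI overall and 400-500 per PPI with high-risk stigmata. Results are planned overall, in high-risk patients and by PPI, with comparisons across strata that include endoscopic findings.
- **Table 2:** outcomes are to be recorded in line with the stated definitions.

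**The concern.** Re-bleeding is one of the four main outcomes, and Objective 2 is one of the two objectives. A patient with a low-risk ulcer who had a diagnostic endoscopy and no endoscopic therapy belongs to the Objective 2 cohort. That patient cannot satisfy a definition that starts from successful endoscopic treatment, even if every clinical sign of a re-bleed is present.

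Three things are at stake:

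- **The overall rate.** It depends on how this gap is handled, and neither literal handling gives the rate that Objective 2 asks for.
- **The contrast by endoscopic findings.** If untreated patients score zero by definition, a difference between strata is partly produced by the definition. A logistic model containing stigmata or treatment could also run into separation.
- **The rates by PPI.** If some abstractors apply the condition and others ignore it, the error varies by centre. Centres are chosen for routinely using a single PPI, so that variation could not be separated from the esomeprazole and pantoprazole rates.

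**Working it through.** **The plan's own figure.** The overall target is 1100 per PPI. The single-proportion precision formula, two-sided 0.05 (the protocol does not state sidedness), gives n = z²p(1−p)/e² = 1.96² × 0.05 × 0.95 / 0.0125² = 1168. This is near the stated 1100 but does not reproduce it. The point does not depend on it; 1100 is used below only to turn rates into counts. At n = 1100 the 95% half-width is 1.29 points for a 5% rate and 1.60 points for an 8% rate.

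**Inputs, all from Statistics.**
- Overall re-bleeding rate R = 8%. The text says more than 8, so this is a floor.
- Ratio of high-risk to overall rate, m = 1.5 to 2, so the high-risk rate is 12-16%.
- High-risk share f = 1/4 to 1/3. Alternatively, if the 400-500 target is read as part of the 1100, f = 36-45%.

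**Share without qualifying stigmata.** 1 − f is 67-75%, or 55-64% with the alternative share. It is a majority either way.

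**Assumption.** All high-risk patients, and only they, are treated endoscopically with success. The protocol gives no treated share.

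**Whole cohort as denominator.** Counted rate = f × m × R. Shortfall = R − f × m × R. Implied rate in patients without stigmata = (R − f × m × R)/(1 − f). With R = 8%, the expected count is 88 per 1100.

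| f | m | High-risk rate | Counted rate | Shortfall (points) | Implied rate without stigmata | Events counted, of 88 |
|---|---|---|---|---|---|---|
| 1/4 | 1.5 | 12% | 3.0% | 5.0 | 6.7% | 33 |
| 1/4 | 2 | 16% | 4.0% | 4.0 | 5.3% | 44 |
| 1/3 | 1.5 | 12% | 4.0% | 4.0 | 6.0% | 44 |
| 1/3 | 2 | 16% | 5.3% | 2.7 | 4.0% | 59 |
| 400/1100 | 1.5 | 12% | 4.4% | 3.6 | 5.7% | 48 |
| 400/1100 | 2 | 16% | 5.8% | 2.2 | 3.4% | 64 |
| 500/1100 | 1.5 | 12% | 5.5% | 2.5 | 4.7% | 60 |
| 500/1100 | 2 | 16% | 7.3% | 0.7 | 1.3% | 80 |

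With the stated share of a quarter to a third, the shortfall of 2.7-5.0 points exceeds both planned errors, 1.25% and 2.5%. Over all eight rows it runs from 0.7 to 5.0, and only the last row falls inside 1.25.

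**Untreated patients dropped from the denominator.** Under the same assumption the rate is f × m × R / f = m × R = 12-16%. That is the treated-patient rate, close to what Objective 1 already reports.

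**The case against.** **The denominator is not stated.** It may stand in a statistical analysis plan that is not at hand. This objection stands as far as direction goes. A reader might infer that the overall rate is certainly biased low, but that needs the whole cohort in the denominator. The Statistics section implies this by promising outcome rates for the cohorts studied, but does not say it. An analysis plan could settle the denominator, yet it could not recover events left unrecorded when the charts were abstracted under the protocol's definition.

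**The wording may simply be loose.** Comparing re-bleeding across endoscopic findings makes little sense if low-risk patients score zero, and Table 2 lists re-bleeding separately from endoscopic treatment. A planned exclusion is therefore unlikely. But Table 2 also ties outcomes to the definitions, and bleeding continuation (item a, 2) speaks of the initial endoscopy where item b speaks of successful treatment. The phrase cannot be assumed to mean any endoscopy.

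**The size is a worst case.** It assumes that every re-bleed in an untreated patient is lost and that treatment coincides with high-risk stigmata. This stands, and it is why the range is given with both shares and its assumption.

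Three further inferences are not supported:

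- **Comparability with the source of the 8%.** The documents do not give that study's definition or denominator, so a loss of comparability cannot be shown. Here 8% serves only as the planning value.
- **Failed first treatment.** Bleeding continuation is a separate main outcome, so not counting these patients as re-bleeds is ordinary separation of endpoints.
- **The transfusion criterion in item a, 2.** It mentions endoscopic therapy, but untreated patients can still qualify through the aspirate or shock criteria.

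**Conclusion.** The point holds as a mismatch between a main outcome and the cohort it must describe. It is an error in a stated rule, not a missing detail. Read literally, the definition gives either an overall rate short by roughly 0.7-5.0 points (whole cohort as denominator) or a treated-patient rate of about 12-16% (untreated patients dropped). Neither is the Objective 2 rate.

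The sizes rest on the protocol's planning figures and on equating successful endoscopic treatment with high-risk stigmata. If abstractors apply the clinical signs to everyone, the error shrinks but may differ between centres. Objective 1 is largely unaffected, and the surgery and mortality definitions do not carry this condition.

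**What to change.** 1. In item b of the outcome definitions, replace the condition on successful endoscopic treatment with: *following initial haemostasis at the index endoscopy, whether spontaneous or achieved by endoscopic treatment*. Carry the same wording into the CRF instructions.
2. State the denominator for each cohort. For the Objective 2 rate use the whole cohort, with the rate among patients with initial haemostasis as a supplement.
3. Report re-bleeding overall and by endoscopic treatment yes/no. Table 2 already collects Forrest class, stigmata and type of therapeutic endoscopy.
4. Optionally, align the transfusion criterion in item a, 2 with that item's opening words.

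The cost is a few sentences and no new variable, provided the wording is settled before the charts are abstracted. The downside is that the reported overall re-bleeding rate may look less favourable.
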